## 10.2.2 Adverse Event Overview

The number and percentage of subjects experiencing TEAEs will be summarized for each treatment group for the following AE categories.:

- Any TEAE
- Any treatment-emergent serious adverse events (SAE)
- Any TEAE leading to discontinuation of study drug
- Any severe TEAE (Grade 3 and above according to National Cancer Institute (NCI) Common Terminology Criteria for Adverse Events (CTCAE) version 5.0)
- Any TEAE related to study drug according to the investigator
- Any treatment-emergent SAE related to study drug according to the investigator
- TEAEs of Special Interest
- Other Safety Topics of Interest
- Any TEAE leading to death
- All Deaths
  - Deaths occurring  $\leq$  30 days after last dose of upadacitinib or  $\leq$  84 days after last dose of dupilumab
  - Deaths occurring  $>$  30 days after last dose of upadacitinib or  $>$  84 days after last dose of dupilumab
  - Related to COVID-19

## 10.2.3 Treatment-Emergent Adverse Events by SOC and/or PT

TEAEs will be summarized and presented using primary MedDRA version 22.1 or later by system organ class (SOC) and preferred terms (PT); by maximum relationship to study drug as assessed by the investigator (e.g., reasonable possibility or no reasonable possibility) and SOC and PT; by maximum toxicity and SOC and PT. The SOCs will be presented in alphabetical order, and the PTs will be presented in alphabetical order within each SOC. Subjects reporting more than one adverse event for a given MedDRA preferred

term will be counted only once for that term (most severe incident for the toxicity tables and most related incident for the relationship tables). A subject who reports more than 1 AE in different SOCs will be counted only once in the overall total. Subjects reporting more than one type of adverse event will be counted only once in the overall total. If the same adverse event occurs multiple times within a subject, the highest severity and level of relationship to investigational product will be reported.

The following summaries of adverse events will be generated:

- All TEAEs
- Treatment-emergent serious adverse events
- Treatment-emergent severe adverse events
- TEAEs related to study drug according to the investigator
- TEAEs leading to discontinuation of study drug
- TEAEs by maximum relationship to the study drug as assessed by the investigator (e.g., reasonable possibility or no reasonable possibility)
- TEAEs by maximum toxicity
- TEAEs leading to death

For summaries of AEs by toxicity, each subject is counted only once according to the maximum toxicity level observed. If a subject has an AE with an unknown toxicity, then the subject will be counted in the toxicity category of "unknown." The only exception is that if the subject has another occurrence of the same AE with the most extreme, non-fatal NCI CTCAE toxicity (i.e., grade 4) or is fatal (grade 5). In this case, the subject will be counted under grade 4 if non-fatal or 5 if fatal. For tables that look at severity instead of toxicity, the subjects that have an unknown NCI CTCAE grade but another occurrence of the same AE that is considered severe (grade  $\geq 3$ ) will be counted under severe.

#### **10.2.4 Treatment-Emergent Adverse Events per Patient-Years of Exposure**

AEs occurring during the entire study will be presented by event rate per 100 patient years. These will be presented by treatment group for the following AE categories.

- Any TEAE
- Any treatment-emergent SAE
- Any TEAE leading to discontinuations of study drug
- Any severe TEAE
- Any TEAE related to study drug according to the investigator
- Any treatment-emergent SAE related to study drug according to the investigator
- TEAEs of Special Interest
- Other Safety Topics of Interest;
- Any TEAE leading to death
- All Deaths
  - Deaths occurring  $\leq 30$  days after last dose of upadacitinib or  $\leq 84$  days after last dose of dupilumab
  - Deaths occurring  $> 30$  days after last dose of upadacitinib or  $> 84$  days after last dose of dupilumab
  - Related to COVID-19

Additional AEs may be considered for tabulation/summary based on recommendations from Clinical and Safety as deemed appropriate.

#### **10.2.5 Deaths, Serious Adverse Events, and Adverse Events Leading to Study Treatment Discontinuation**

SAEs (including deaths) and AEs leading to study drug discontinuation will be presented in listing format. SAEs and AEs leading to study drug discontinuation will be summarized by SOC and PT.

In addition, for each treatment group, the event rate leading to per 100 patient-years of exposure will be calculated for each SOC and each PT for each treatment emergent SAE and TEAEs leading to discontinuation of study drug.

### **10.2.6 Adverse Events of Special Interest**

Adverse events of special interest will be summarized by SOC and PT and listing format and will be based on standard or company MedDRA queries (SMQs or CMQs) 1) from Baseline to Week 16 visit and 2) the entire upadacitinib treatment period, respectively.

Adverse events of special interest are categorized as follows:

- Serious infections
- Opportunistic infections excluding tuberculosis and herpes zoster
- Herpes Zoster
- Active Tuberculosis
- Anemia
- Neutropenia
- Lymphopenia
- Renal Dysfunction
- Hepatic disorder
- Creatine Phosphokinase Elevations (CPK; adolescents only)
- Possible Malignancy\*
- Malignancy
- Non-melanoma skin cancer (NMSC)
- Malignancy excluding NMSC
- Lymphoma
- Adjudicated MACE
- Adjudicated VTE
- Adjudicated gastrointestinal perforations

\* Possible Malignancy is used for surveillance and safety monitoring for both clinical trial and post marketing data and will not be included as AESI in in text tables for any safety document.

Detailed information about the search criteria is provided in [Appendix B](#).

### **10.2.7 Adverse Events of Other Safety Topics of Interest**

Adverse Events of Other Safety Topics of Interest specifically for this study will be summarized by SOC and PT and listing format and will be based on standard or company MedDRA queries (SMQs or CMQs or selected PTs) in Period 1. Detailed information about the search criteria is provided in [Appendix G](#). The listings of Adverse Events of Other Safety Topics of Interest will be provided.

### **10.3 Analysis of Laboratory Data**

Data collected from central and local laboratories, including additional laboratory testing due to an SAE, will be used in all analyses. The clinical laboratory tests defined in the protocol operations manual (e.g., hematology and clinical chemistry) will be summarized.

For the analysis of laboratory data, values observed up to 30 days after the last dose of upadacitinib or 84 days after the last dose of dupilumab will be included.

#### **Analysis of Quantitative Laboratory Parameters (Hematology, Chemistry and Urinalysis)**

Raw values and change from Baseline (percent change if applicable) to each applicable post-baseline visit will be summarized for selected laboratory variables. At each visit, the following descriptive statistics will be presented by treatment groups: number of observations, Baseline mean (Standard deviation, SD), visit mean (SD), change from Baseline mean (SD), standard error, and the 95% confidence interval of the mean change from Baseline.

#### **Shift Table Analyses**

Selected laboratory parameters will be tabulated using shift tables from Baseline to the worst value by NCI CTCAE in Period 1 for the Safety 1 Population and during the administration of upadacitinib for the All UPA Population. Selected lipid parameters will

be summarized using National Cholesterol Education Program (NCEP) Adult Treatment Panel III (ATPIII) guidelines and details can be found in [Appendix E](#). Similar shift tables will be provided to summarize shifts from Baseline to the final post-baseline value in Period 1 for the Safety 1 Population and during the administration of upadacitinib for the All UPA Population. Here, the Upadacitinib Baseline is defined as the last observation prior to the first dose of upadacitinib. The criteria in shift table are defined using CTCAE 4.03.

### **Potentially Clinically Important Laboratory Values**

Laboratory abnormalities will be evaluated based on Potentially Clinically Important (PCI) criteria (NCI CTCAE V4.03 criteria of Grade 3 or above). For each laboratory PCI criterion, the number and percentage of subjects who have a laboratory value meeting the criteria will be summarized. Listings will be provided to summarize subject-level laboratory data for subjects meeting PCI criteria. The PCI criteria are defined in [Appendix C](#) using CTCAE 4.03.

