The efficacy and safety of upadacitinib 15 mg and 30 mg QD was assessed in 3 Phase 3 randomized, double-blind, multicenter studies (MEASURE UP 1, MEASURE UP 2, and AD UP) in a total of 2584 subjects (12 years of age and older).⁶⁻⁸ A significantly greater proportion of subjects treated with upadacitinib 15 mg or 30 mg QD achieved validated Investigator's Global Assessment for AD (vIGA-AD) 0 or 1, Eczema Area and Severity Index (EASI) 75, EASI 90, EASI 100, Dermatology Life Quality Index (DLQI) 0 or 1, or a ≥ 4 -point improvement on the Worst Pruritus Numerical Rating Scale (WP-NRS) compared to placebo at Week 16. Rapid improvements in skin clearance and itch were also achieved. Results at Week 16 were maintained through Week 52 in subjects treated with upadacitinib 15 mg or 30 mg QD.

Adverse events (AEs) such as infections including herpes zoster reactivation, major adverse cardiovascular events (MACE defined as cardiovascular death, non-fatal myocardial infarctions, and non-fatal strokes), thrombosis, malignancies, hypersensitivity (serious anaphylactic reaction and angioedema), gastrointestinal perforation, bone fracture, and some laboratory abnormalities have been observed in patients receiving JAK inhibitors including upadacitinib.

An increased risk of infections including opportunistic infections (e.g., mucosal candida infections) and herpes zoster, non-melanoma skin cancer (NMSC), and abnormal laboratory changes (e.g., elevations of serum transaminases, lipids, creatine phosphokinase [CPK], and reductions in hemoglobin and white blood cells [WBC]) have been observed with upadacitinib therapy.

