7.5 Statistical Analyses for Safety

The safety analyses will be carried out using the Safety Population and will be based on treatments the subjects actually received. Safety will be assessed by AEs, physical examination, laboratory assessments, and vital signs. Note that missing safety data will not be imputed.

Adverse events will be coded using the Medical Dictionary for Regulatory Activities (MedDRA). Treatment-emergent adverse events (TEAEs) are defined as those that began or worsened in severity after the first dose of study drug and no more than 5 half-lives of the drug after the last dose of study drug. Specifically, 30 days will be used for upadacitinib, and 84 days (12 weeks) will be used for dupilumab. The number and percentage of subjects experiencing TEAEs will be tabulated using system organ class and preferred term, overall and by severity and by relationship to the study drug as assessed by the investigator by the Period using the Safety_1 population and Safety_2 population, respectively. Summaries (including percentages and events per 100 patient years) of TEAEs, AESIs, SAEs, deaths, and AEs leading to discontinuation will be provided in both Periods.

For laboratory tests and vital signs, mean change from baseline and percentage of subject with evaluations meeting pre-defined Potentially Clinically Important criteria will be summarized in both Periods. For selected lab parameters, a listing of all subjects with any laboratory value above Grade 3 of Common Toxicity Criteria will be provided. Additional details for the safety analysis will be provided in the SAP.

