### **Liver Function Tests**

For the purpose of assessing for potential Hy's law cases, the frequencies and percentages of subjects with post-baseline liver function test values that meet the PCI criteria (defined in [Appendix C](#)) will be presented in Period 1 using the Safety 1 Population and during the administration of upadacitinib using the ALL UPA Population.

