**Table C-4. Criteria for Potentially Clinically Important Vital Sign Values**

Vital Sign	Category	Criteria for Potential Clinically Significant Vital Signs
Systolic blood pressure	Low	Value $\leq 90$ mmHg and decrease $\geq 20$ mmHg from Baseline
	High	Value $\geq 160$ mmHg and increase $\geq 20$ mmHg from Baseline
Diastolic blood pressure	Low	Value $\leq 50$ mmHg and decrease $\geq 10$ mmHg from Baseline
	High	Value $\geq 100$ mmHg and increase $\geq 10$ mmHg from Baseline
Pulse	Low	Value $\leq 50$ bpm and decrease $\geq 15$ bpm from Baseline
	High	Value $\geq 120$ bpm and increase $\geq 15$ bpm from Baseline
Weight (adults)	High	$> 7\%$ increase from Baseline
	Low	$> 7\%$ decrease from Baseline
Weight (Adolescents)	Low	$> 7\%$ decrease from Baseline

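### The laboratory PCI count has no worsening condition and no stated post-baseline start, so persistent pre-existing CPK, lipid and glucose abnormalities are counted as on-treatment findings

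*SAP*

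**What the plan says.** SAP 10.3, Potentially Clinically Important Laboratory Values, defines PCI as CTCAE v4.03 Grade 3 or above and gives the counting rule: "For each laboratory PCI criterion, the number and percentage of subjects who have a laboratory value meeting the criteria will be summarized". It adds subject-level listings of PCI cases. Tables C-1 and C-2 in Appendix C supply the cut-offs, for example CPK above 5.0 × ULN, triglycerides above 5.7 mmol/L, total cholesterol above 10.34 mmol/L and glucose below 2.2 or above 13.9 mmol/L. None refers to Baseline.

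The opening of SAP 10.3 sets the end of the laboratory window but no start: "values observed up to 30 days after the last dose of upadacitinib or 84 days after the last dose of dupilumab will be included". Protocol 7.5 says the "percentage of subject with evaluations meeting pre-defined Potentially Clinically Important criteria will be summarized in both Periods".

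Two related rules are tighter. The liver summary in SAP 10.3 counts "subjects with post-baseline liver function test values that meet the PCI criteria". In Table C-4, every vital-sign and weight criterion includes a change from Baseline; high systolic pressure, for instance, needs both a value of at least 160 mmHg and a rise of at least 20 mmHg.

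**The concern.** A PCI table is read as a summary of what happened on treatment. Without a comparison to Baseline, a subject who entered the trial with a Grade 3 CPK or triglyceride value and stayed there is indistinguishable from one who developed it on study drug.

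The exposed analytes are ones that matter here. Protocol 2.2 names lipid and CPK elevations among the changes observed with upadacitinib. CPK elevation is an adverse event of special interest for adolescents only (Protocol 6.1, SAP 10.2.6), so for adults the laboratory tables carry more of the weight. Safety is part of the primary study objective (Protocol 3.1).

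In the ALL UPA population there is a second problem. It includes subjects switched from dupilumab at Week 16, and the PCI rule does not say which baseline applies to them.

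**Working it through.** **1. Does any text supply the missing conditions?**

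| Rule | Post-baseline stated | Worsening required |
|---|---|---|
| Laboratory PCI (SAP 10.3, Tables C-1 and C-2) | No | No |
| Liver function PCI (SAP 10.3, Table C-3) | Yes | No |
| Vital-sign and weight PCI (Table C-4) | Implied by the change criterion | Yes |
| Laboratory shift tables (SAP 10.3) | Yes | Baseline is shown alongside |

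Reporting by period, as in Protocol 7.5, points to on-treatment values. However, the Baseline draw is on Day 1 (Protocol Appendix D), so the wording does not clearly exclude it. No text supplies a worsening condition for the analytes in Tables C-1 and C-2.

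**2. Which analytes are exposed?** Compare the entry limits in Protocol 5.1 with the PCI cut-offs.

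| Analyte | Entry limit | PCI cut-off |
|---|---|---|
| AST, ALT | ≤ 2 × ULN | > 5.0 × ULN |
| Hemoglobin | ≥ 9 g/dL | < 8.0 g/dL |
| WBC | ≥ 2.5 × 10⁹/L | < 2.0 × 10⁹/L |
| Neutrophils | ≥ 1.2 × 10⁹/L | < 1.0 × 10⁹/L |
| Lymphocytes | ≥ 0.75 × 10⁹/L | < 0.5 × 10⁹/L |
| Platelets | ≥ 100 × 10⁹/L | < 50 × 10⁹/L |
| CPK, triglycerides, cholesterol, glucose | none | as quoted above |

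The first six rows are protected at entry. The last is not.

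**3. Size.** The plan states no figure for PCI rates, so there is nothing to reproduce. Inputs: 440 per arm (Protocol 4.1); baseline prevalence b, equal in both arms by randomisation; and new-onset rate p among the rest. Neither b nor p is in the documents; both are assumptions.

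- Reported rate = b + (1 − b)p
- Risk difference = (1 − b)(p_U − p_D)
- Ratio = [b + (1 − b)p_U] / [b + (1 − b)p_D]

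Assuming p_U = 2% and p_D = 1% (ratio 2.0, difference 1 point):

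| b | Pre-existing per arm (440b) | Upadacitinib | Dupilumab | Difference (points) | Ratio |
|---|---|---|---|---|---|
| 0.5% | 2.2 | 0.5 + 0.995 × 2 = 2.49% | 0.5 + 0.995 × 1 = 1.495% | 0.995 | 1.67 |
| 1% | 4.4 | 1 + 0.99 × 2 = 2.98% | 1 + 0.99 × 1 = 1.99% | 0.99 | 1.50 |
| 2% | 8.8 | 2 + 0.98 × 2 = 3.96% | 2 + 0.98 × 1 = 2.98% | 0.98 | 1.33 |

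Assuming instead 4% versus 1%, the ratio of 4.0 becomes 3.00, 2.49 and 1.99 at the same three values of b, with differences of 2.985, 2.97 and 2.94 points. A count of new-onset cases only, (1 − b)p, keeps the ratio at 4.0 and gives the same differences. As a gauge of noise, the nominal power of a two-sided 0.05 comparison at 440 per arm would be 74%, 67% and 56%, against about 81% for the new-onset count.

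These are upper bounds on the dilution. They hold if Day 1 values are counted, or if every pre-existing abnormality persists. If only half persist, the effective b is roughly halved.

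**4. Can other planned outputs separate the cases?** Partly. The shift tables and change-from-Baseline summaries cover selected parameters that the SAP does not list. Lipids are summarised in the NCEP categories of Appendix E, where the top class starts at 2.26 mmol/L for triglycerides and 6.21 mmol/L for total cholesterol. The PCI cut-offs are 5.7 and 10.34. A triglyceride rise from 3.0 to 6.0 stays in the top class, and so does a stable 6.0. Both meet PCI, and the categories cannot tell them apart.

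**5. ALL UPA.** The shift-table paragraph defines an Upadacitinib Baseline as the last observation before the first upadacitinib dose. The PCI paragraph does not use it. A switcher who reached PCI level before that dose and stayed there is counted under upadacitinib.

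**The case against.** The strongest reply is that the SAP is silent rather than wrong. Nowhere does it say that Baseline values count. Protocol 7.5 reports by period, and SAP Table 1 ties ALL UPA to the time of upadacitinib administration. A reader might infer that Day 1 values themselves enter the count; the documents do not go that far, and a sensible programmer would probably exclude them. This stands. It leaves the missing worsening condition as the firm part of the point, because a persistent abnormality is counted even on a strictly post-baseline reading.

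Second, the liver rule also has no worsening condition, so a comparison with Baseline is not the SAP's norm for laboratory PCI counts. This is true; only the vital-sign and weight criteria have it. But AST and ALT are capped at entry, which CPK, lipids and glucose are not.

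Third, entry is controlled in other ways. Protocol 5.1 requires good health judged on Screening results and excludes unstable conditions and subjects the investigator finds unsuitable. These make Grade 3 entry values less likely but do not rule them out.

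Fourth, shift tables, change-from-Baseline summaries and PCI listings are planned. They do help. A shift table by CTCAE grade would separate new from old CPK cases if CPK is among the selected parameters. They do not resolve the lipid cut-offs, and listings leave the reader to recount by hand.

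**Conclusion.** The point holds as a gap in descriptive safety reporting. For analytes with no numeric entry limit, the planned PCI percentages mix new and persistent pre-existing abnormalities, and ALL UPA can attribute to upadacitinib what was present before its first dose. Both arms' percentages are inflated, the ratio is diluted and precision is lost. On the illustrative assumption of 2% versus 1% new onset and 0.5% to 2% baseline prevalence, the ratio falls from 2.0 to no lower than 1.67 to 1.33. The true size is unknown, because the documents give neither the prevalence nor the new-onset rates.

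A reader might infer that the rule hides a difference between the arms. It does not: with prevalence balanced by randomisation, the risk difference shrinks only by the factor (1 − b), from 1 point to 0.98 at b = 2%. The SAP plans counts and percentages for PCI, with no ratio and no between-arm test. No primary or ranked endpoint and no type I error is affected. The ALL UPA issue involves no randomised comparison and concerns only switchers whose abnormality persists.

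**What to change.** In SAP 10.3, Potentially Clinically Important Laboratory Values, count subjects with at least one post-baseline value meeting the criterion in the period and population concerned. Show that count separately for subjects who did not and who did meet the criterion at Baseline. For ALL UPA, and for subjects switched from dupilumab in Period 2, use the Upadacitinib Baseline already defined for the shift tables. Treat a missing Baseline as not meeting the criterion, so that no potential new case is set aside.

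Splitting the count is preferable to requiring a worse CTCAE grade than at Baseline, which would drop subjects who worsen within the same grade. The split loses no one: the two rows add up to the full post-baseline count. The cost is one sentence in the SAP, one flag in the program and one extra row per criterion in the table.

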### **Liver Function Tests**

For the purpose of assessing for potential Hy's law cases, the frequencies and percentages of subjects with post-baseline liver function test values that meet the PCI criteria (defined in [Appendix C](#)) will be presented in Period 1 using the Safety 1 Population and during the administration of upadacitinib using the ALL UPA Population.

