3 OBJECTIVES AND ENDPOINTS

3.1 Objectives, Hypotheses, and Estimands

Objectives

Primary

The primary study objective, related to Study Period 1, is to assess the efficacy and safety of upadacitinib, initiated at 15 mg once daily (QD) and dose adjusted based on clinical response, compared with dupilumab as per its label.

An additional objective, related to Study Period 2, is to assess the efficacy and safety of upadacitinib, initiated at 15 mg QD and dose adjusted based on clinical response, in subjects with inadequate response to dupilumab.

The primary efficacy objective is based on the achievement of a composite endpoint of at least a 90% reduction in EASI from baseline (EASI 90) and a Worst Pruritus Numerical Rating Scale of 0 or 1 (WP-NRS 0/1) at Week 16 with the treatment of upadacitinib compared with dupilumab per its label in the Intent-to-Treat (ITT) Population, which consists of all randomized subjects (Section 7.2).

Secondary

The secondary efficacy objectives are based on ranked secondary endpoints as defined in Section 3.3 with the treatment of upadacitinib compared with dupilumab in the ITT Population.

Hypotheses and Estimands for the Primary and Ranked Secondary Endpoints

The hypothesis corresponding to the primary efficacy endpoint (Section 3.2) is:

- The proportion of subjects achieving both EASI 90 and WP-NRS 0/1 at Week 16 in those treated with upadacitinib is greater than those treated with dupilumab.

The estimand corresponding to the primary endpoint is defined using the composite variable strategy, as follows:

- Difference in the proportion of subjects achieving both EASI 90 and WP-NRS 0/1 at Week 16 without the use of rescue medication, regardless of treatment discontinuation, between upadacitinib and dupilumab in the adolescent and adult subjects with moderate to severe AD who have inadequate response to systemic therapy.

The hypotheses and estimands corresponding to the ranked secondary endpoints are summarized below.

- Hypotheses: the proportion of subjects achieving each ranked endpoint in those treated with upadacitinib is greater than those treated with dupilumab

- Estimands: Difference in proportion of subjects achieving each of ranked secondary endpoints without the use of rescue medication, regardless of treatment discontinuation, between upadacitinib and dupilumab in the adolescent and adult subjects with moderate to severe AD who have inadequate response to systemic therapy.

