## **10.4 Analysis of Vital Signs**

Vital sign measurements of systolic and diastolic blood pressure, pulse rate, and body temperature will be summarized.

Each vital sign variable will be summarized for all time points (starting with Baseline) with the number of non-missing observations, mean and standard deviation, median, minimum and maximum. Mean change from Baseline to each applicable post-baseline visit in both Periods 1 and 2 will be summarized for each vital sign variable, with the

number of observations, Baseline mean, and visit mean. The change from Baseline mean, standard error, and 95% confidence interval will be presented for the mean change from Baseline by treatment group in Period 1 and Period 2.

Vital sign variables will be evaluated based on potentially clinically important (PCI) criteria ([Appendix C](#)) in Period 1 and for the ALL UPA Population. For each vital signs PCI criterion, the number and percentage of subjects who have at least one vital sign value meeting the criteria will be summarized. Listings will be provided to summarize subject-level vital sign data for subjects meeting PCI criteria.

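### The SAP gives liver and vital-sign PCI percentages only for Period 1 and the pooled ALL UPA set, although Protocol 7.5 commits to laboratory and vital-sign PCI percentages in both periods

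*SAP*

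**What the plan says.** Protocol 3.1 sets a second objective: "An additional objective, related to Study Period 2, is to assess the efficacy and safety of upadacitinib" in subjects with an inadequate response to dupilumab. Protocol 7.5 then says, for laboratory tests and vital signs together, that mean change and the "percentage of subject with evaluations meeting pre-defined Potentially Clinically Important criteria will be summarized in both Periods".

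The SAP creates the population for this. Table 1 defines Safety 2 for Period 2, with two groups: Upadacitinib/Upadacitinib 30 mg and Dupilumab/Upadacitinib. It also defines ALL UPA, with columns for 15 mg, 30 mg and Any UPA.

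The PCI tables are specified as follows.

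- Liver (SAP 10.3, Liver Function Tests): percentages meeting the criteria "will be presented in Period 1 using the Safety 1 Population and during the administration of upadacitinib using the ALL UPA Population".
- Vital signs (SAP 10.4): PCI evaluation "in Period 1 and for the ALL UPA Population". Table C-4, which supplies the criteria, also covers weight.
- General laboratory PCI (SAP 10.3, Potentially Clinically Important Laboratory Values): a number and percentage per criterion, with no period or population named.

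**The concern.** Followed as written, the SAP omits two Period 2 summaries that fall within the protocol's commitment. Liver tests are laboratory tests, so they come under Protocol 7.5 as plainly as vital signs do. The omission falls on the group that the Period 2 objective is about. A reader of the report could not see what percentage of dupilumab switchers met a liver or vital-sign threshold after starting upadacitinib.

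The SAP is also uneven on this. Adverse events are summarized for Safety 2 (SAP 10.2), and vital-sign mean changes are given for both periods (SAP 10.4). The liver and vital-sign threshold tables, which are meant to show outliers, are the ones that leave Period 2 out.

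**Working it through.** The plan has no figure to reproduce here. The check is a comparison of texts, followed by an illustration of what pooling hides.

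**Which outputs are promised, and which are restricted**

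- Vital-sign and weight PCI percentages: the protocol says both periods, the SAP says Period 1 and ALL UPA. This is a direct conflict.
- Liver PCI percentages: the protocol says both periods for laboratory tests, the SAP says Period 1 and ALL UPA. This is a conflict.
- General laboratory PCI percentages: the protocol says both periods, the SAP is silent. This is ambiguous but compatible with the protocol.

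**Does the general laboratory summary cover the liver gap?** Only in part. It describes its criteria as CTCAE Grade 3 or above. The chemistry criteria in Table C-2 include AST and ALT above 5 × ULN, but have no bilirubin row. The criteria of at least 3 × ULN, alone or with concurrent raised bilirubin, are in Table C-3. That is the liver table, and the SAP introduces the liver analysis as the one for potential Hy's law cases.

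**Does ALL UPA stand in for Period 2?** No, for two reasons.

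1. Its columns do not separate prior dupilumab from randomized upadacitinib.
2. It mixes exposure lengths: up to about 16 weeks for switchers and for upadacitinib subjects who finish at Week 16, and up to about 32 weeks for upadacitinib subjects who go on to Period 2.

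Subtraction does not recover the switchers' rate either. Let x be the Any UPA subjects meeting a criterion and y the upadacitinib subjects meeting it in Safety 1. With the same assessment windows, x − y counts switchers plus upadacitinib-arm subjects who first met the criterion in Period 2. That is an upper bound for switchers, not an estimate.

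**Illustration.** The only input from the documents is 440 planned per arm. Assume that all 440 upadacitinib subjects are dosed and that a fraction f of the dupilumab arm switches, so s = 440 × f.

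- Share of Any UPA = s / (440 + s). At f = 0.20, 88/528 = 16.7%. At f = 0.60, 264/704 = 37.5%.
- Pooled rate = (p₁s + p₀ × 440) / (440 + s), where p₁ is the assumed rate in switchers and p₀ the rate in the others.
- With p₁ = 3% and p₀ = 1%: (2.64 + 4.40)/528 = 1.3%, up to (7.92 + 4.40)/704 = 1.75%.
- With p₁ = 6% and p₀ = 2%: (5.28 + 8.80)/528 = 2.7%, up to (15.84 + 8.80)/704 = 3.5%.
- Reported alone, zero events among switchers would give an approximate upper 95% bound of 3/s: 3/88 = 3.4%, down to 3/264 = 1.1%.

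The switch fractions and event rates are assumptions, and the threefold excess is put in by hand. The figures show only that the pooled column cannot display the group's own rate.

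**The case against.** The best reply is that little is lost.

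- The switchers' data on upadacitinib are in ALL UPA.
- SAP 10.3 and 10.4 plan subject-level listings of subjects meeting PCI criteria, with no period limit. For rare liver cases, individual review is informative.
- Laboratory change from baseline is by treatment group at each applicable visit, without a period limit, and vital-sign mean changes cover Period 2.
- Period 2 is descriptive, so no test changes.

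All of this stands. It rules out saying that the plan reports nothing on this group. It does not supply the group percentage that Protocol 7.5 commits to. Whether the laboratory listing takes in the Table C-3 criteria also depends on the same loosely worded subsection.

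Three stronger readings are tempting, and the documents do not support them.

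- A reader might infer that the laboratory shift tables, planned "in Period 1 for the Safety 1 Population and during the administration of upadacitinib for the All UPA Population", also break the protocol's promise. Protocol 7.5 does not mention shift tables.
- A reader might say the same of other safety topics, whose SOC and preferred-term summary is "based on standard or company MedDRA queries (SMQs or CMQs or selected PTs) in Period 1". The protocol does not promise that table for Period 2. The topics are also in the adverse event overview and exposure-adjusted rates (SAP 10.2.2 and 10.2.4), which SAP 10.2 applies to Safety 2.
- A reader might infer an undeclared departure because no text appears under SAP 14.1. Text may be missing from the available copy, so nothing can be concluded from that.

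**Conclusion.** The conflict is real but narrow. It covers two outputs, the liver PCI percentages and the vital-sign and weight PCI percentages. For these the SAP names fewer periods than Protocol 7.5, and the Dupilumab/Upadacitinib group has no group-level result. The general laboratory PCI summary needs clarification. It would be wrong to read it as limited to Period 1, or to conclude that Period 2 has no laboratory abnormality percentages at all.

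The textual conflict rests on no assumption. Its practical size cannot be fixed from the documents, because neither the number of switchers nor any event rate is given. The 17% to 38% share holds only under the assumed 20% to 60% switch rate. Nothing here suggests a hidden safety signal, and the primary and ranked secondary analyses are untouched. The point deserves correction because it concerns a stated safety objective and costs little.

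**What to change.** In SAP 10.3 (Liver Function Tests) and in the PCI paragraph of SAP 10.4, add Period 2 for the Safety 2 Population, by the Table 1 groups. Where a criterion needs a change from baseline, as in Table C-4, use for Dupilumab/Upadacitinib subjects the Upadacitinib Baseline already defined under Shift Table Analyses: the last observation before the first upadacitinib dose. In the general laboratory PCI subsection, state that the summary covers Period 1 (Safety 1), Period 2 (Safety 2) and ALL UPA. Keep the existing tables.

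If the restriction is intended, record and justify it as a change from Protocol 7.5. Safety 2 shift tables and a Period 2 SOC and preferred-term table of other safety topics are optional additions.

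The cost is SAP wording and a re-run of existing table programs. Chemistry, hematology, vital signs and weight are already scheduled at Weeks 20 and 32 (Protocol Appendix D), so no new data are needed. The downside is a few more descriptive tables.
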